6.0 Enrollment/Randomization

The surgical schedule will be assessed daily to identify patients scheduled for surgery who may be eligible to participate in this study. A member of the research team, either principal investigator, co-investigator, or study coordinator will approach the potential subject the day of their scheduled procedure. They will conduct the visit in a private area such as a patient's room, secluded hospital room, or an area free from the general public. All study procedures will be reviewed, questions answered, and the subject will be given ample time to discuss and determine if they will sign the consent to participate in the study.

We plan to enroll 110 subjects in this study. Patients will be randomized to either the control or the study group.

7.0 Study Procedures

As noted above, following enrollment on the day of surgery, the Sedline device will be placed on the patient just prior to the induction of anesthesia. Anesthesia

will then be induced, and surgery will proceed as usual. Images will be captured of the display of the Sedline monitor while under anesthesia during the surgical procedure using a recording device. The study group will have the Sedline readings visible to the anesthesiologist in the room and will use the Sedline to guide anesthetic depth. The control group will have the monitor out of view and not visible to the anesthesiologist, but the images of the Sedline monitor will be recorded.

Once the procedure is complete, the Sedline monitor will be removed from the patient and the collection of images will be stopped prior to the patient exiting the operating room.

Following the finalization of the anesthetic records, the desired data will be collected from the anesthetic record. The images of the Sedline readings will also be reviewed by investigators to confirm an appropriate depth of anesthetic was achieved in the study group.

8.0 Study Calendar

We will begin to enroll patients once we receive approval for study commencement from the IRB and following selection/training of the anesthesiology study team. We plan to enroll 110 patients total. Following data collection of the last patient the study will be closed.

9.0 Reportable Events

Patients will be monitored by the primary team during the postoperative period, and any adverse events or unanticipated problem will be reported to the anesthesia service and research team. All unanticipated problems will be reported to the IRB committee using the prompt reporting form.

10.0 Data Safety Monitoring

In order to protect the privacy of our patients, any data which has identifiable patient data attached to it will be stored in the REDcap system. Of note, the images obtained from the Sedline monitor display will not contain ANY identifiable patient data (these images will be stored on a research computer).

11.0 Study Withdrawal/Discontinuation

The patient can withdraw from the study at any time by contacting the research team or the anesthesia service.

12.0 Statistical Considerations

Primary outcome: total average percent of volatile anesthetic (sevoflurane) utilized while subjects are under anesthesia.

Secondary outcomes: total dosage of hypnotic and opioid agents administered while in the maintenance phase of anesthesia. These agents include midazolam, lorazepam, diazepam, fentanyl, sufentanil, ketamine, propofol, morphine, and hydromorphone during the maintenance phase of anesthesia. Additional secondary outcomes measured will include episodes of hypotension, episodes of burst suppression, and total dosage of vasopressors and hypnotic agents.

Statistical analysis will be performed using a standard statistical program (SAS or Stata). All data will be summarized (either means and standard deviations or medians and quartiles for continuous variables; frequencies and percentages for categorical variables) by treatment group. Demographic data will be compared between the two groups using t-test or Wilcoxon rank sum test as appropriate for continuous variables, and chi-square tests or Fisher's exact test for categorical variables as appropriate. The primary outcome, total average percent of volatile anesthetic (sevoflurane) utilized along with secondary outcomes of total dosage of hypnotic agents administered, will be compared between the two groups using t-test or Wilcoxon rank sum test as appropriate. To account for the possible effects of covariates age, sex, and BMI and anesthesiologist, a mixed model with a random effect for anesthesiologists will be employed. Here we could treat surgery type and duration as fixed effects if needed. The secondary outcome of episodes of hypotension which will be compared using chi-square tests or Fisher's exact test for the occurrence of hypotension. Distributions of the continuous variables will be examined, and a transformation of the data (e.g. natural logarithm) or nonparametric tests will be used as necessary. A 5% significance level will be used for all comparisons.

From a similar study using an outcome (minimum alveolar concentration or MAC) comparable to ours we were able to estimate a coefficient of variation for total average percent of volatile anesthetic to be 0.15.⁴ Working with a feasible sample size of 44 per group and using a power of 90%, 5% significance level, and employing a two-sided test, the study will be able to detect a reduction of 10% in for total average percent of volatile anesthetic between the two groups. Assuming a dropout rate of up to 20%, we will enroll up to 55 patients per group for this study. Here we used a “Tests for the Ratio of Two Means” using sample size software PASS 2019.

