3.2 Secondary Outcome Measures

The secondary outcomes measured will be the total dosage of hypnotic agents administered while in the maintenance phase of anesthesia. These agents include: midazolam, lorazepam, diazepam, fentanyl, sufentanil, ketamine, propofol, morphine, and hydromorphone. Additional secondary outcomes measured will include episodes of hypotension (this will be defined as an episode of mean arterial pressure of <65 mmHg), total dosage of vasopressors (such as phenylephrine, ephedrine, vasopressin, or norepinephrine), and the occurrence of EEG isoelectricity, or burst suppression. SedLine images will be recorded for both groups in order to compare rates and duration of burst suppression events. Of note, if the patient has a functioning arterial line in place, we will use measurements from this in preference to a non-invasive blood pressure cuff).

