4.0 Eligibility Criteria

4.1 Inclusion Criteria

- Patients undergoing a scheduled surgery (laparotomy, hepatobiliary surgery, gynecologic surgery, and/or urologic surgery procedures) at Indiana University Health University Hospital that is expected to have at least a 3 day post-operative hospital stay.
- ASA class 1, 2, 3, or 4.
- Age 65 years or older.
- Male or Female
- Surgical procedure requiring general anesthesia.

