5.0 Study Design

[figure not shown]
- Prior to study commencement, select anesthesiologists from the Indiana University Health University Hospital Anesthesia Group will be trained on usage and interpretation of the Sedline. Training for this group of providers will include a PowerPoint presentation recording presented by [name] to aid in interpretation of the Sedline data. Representatives from the study will also be available as needed to answer questions as they arise. They will also be given certain guidelines for anesthetic administration based on the processed EEG findings. These will include the following:
 - Usage of sevoflurane as the primary anesthetic agent
 - Reducing sevoflurane dosage if the EEG indicates signs of burst suppression (excessive anesthetic depth), if the PSI on the Sedline reads less than 25, or if hypotension is occurring and the anesthesia provider believes that depth of anesthesia may be a contributing factor.
 - Increasing sevoflurane dosage if the EEG pattern is not consistent with general anesthesia (not enough depth of anesthetic).
- We anticipate 5-10 anesthesiologists being included in this group. Given that this group of anesthesiologists will be assigned to both groups (study and control), the size of the groups, and the instructions regarding the maintenance phase of anesthesia, diazepam, and dexmedetomidine we anticipate the difference in practice patterns between providers will not affect the data. We will discourage the use of nitrous oxide as well as IV anesthetics including midazolam. In the control group, the anesthesiologist will be asked to provide the anesthetic as he or she would under normal care with the exception of avoidance of nitrous oxide and IV anesthetics during the maintenance phase of anesthesia. We anticipate

that the surgical procedures included in this study will be similar enough that the type of surgical procedure will not affect anesthetic dosing.

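### Do the secondary total-dose outcomes need a conversion rule, a committed duration adjustment and a rule for zero doses?

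*Combined protocol and SAP*

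**What the plan says.** Section 3.2 makes total hypnotic dose during maintenance a secondary outcome and lists the drugs: "These agents include: midazolam, lorazepam, diazepam, fentanyl, sufentanil, ketamine, propofol, morphine, and hydromorphone". It adds the "total dosage of vasopressors (such as phenylephrine, ephedrine, vasopressin, or norepinephrine" and similar agents. Section 12.0 repeats the drug list under hypnotics and opioids and names the test: "total dosage of hypnotic agents administered, will be compared between the two groups using t-test or Wilcoxon rank sum test as appropriate".

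Section 12.0 then says that, to account for age, sex, BMI and anesthesiologist, "a mixed model with a random effect for anesthesiologists will be employed", and adds: "Here we could treat surgery type and duration as fixed effects if needed". It does not name the outcomes that this model covers. Distributions are to be inspected, with a transformation (the natural logarithm is given as an example) or a nonparametric test where needed. No test or time window is tied specifically to vasopressor dose.

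Two other sections matter. Eligible operations are "laparotomy, hepatobiliary surgery, gynecologic surgery, and/or urologic surgery procedures" (section 4.1), so case length will probably vary. Section 5.0 says: "We will discourage the use of nitrous oxide as well as IV anesthetics including midazolam". It also asks for "avoidance of nitrous oxide and IV anesthetics during the maintenance phase of anesthesia" in the control group, so zero totals are likely for several listed drugs.

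**The concern.** There are three apparent defects.

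- **Outcome.** Without a unit, grouping or conversion, a literal total over nine drugs would be governed by whichever drug has the largest milligram doses.
- **Duration.** A cumulative dose may grow with case length. A two-sample test that ignores length then carries avoidable noise, and the covariate that would remove it is optional.
- **Zeros.** The only transformation named is undefined at zero. Dropping the zeros would leave a comparison of users only, which is no longer the randomised comparison.

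These outcomes show whether lower sevoflurane was offset by other drugs and whether vasopressor use fell. A noisy or ill-defined result would weaken that reading. The primary outcome is an average percent and is not exposed to any of this.

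**Working it through.** **The plan's own figure.** Section 12.0 gives a sample size for the primary outcome only. With CV 0.15 and ratio 0.90, the log-scale SD is √ln(1 + 0.15²) = 0.1492 and the difference is |ln 0.90| = 0.1054. The noncentral t distribution gives 44 per group (power 90.6%), and 44/0.8 = 55 enrolled. The plan's figures reproduce, but they do not bear on the dose outcomes, for which no figure is stated. Everything below except the 44 per group therefore rests on assumed inputs.

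**Raw sums.** If one drug's mean milligram dose is k times another's, a 25% cut in the smaller moves the sum by 0.25/(1 + k): 2.3% for k = 10, 0.25% for k = 100, 0.025% for k = 1000. A raw sum would indeed be useless. But sections 3.2 and 12.0 list the agents one by one and never say that amounts are added across them. Section 12.0 speaks of secondary outcomes in the plural, which fits a total for each drug.

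**Duration, no zeros.** Assumptions: hourly-dose CV 0.5, duration CV 0.4, true ratio 0.75, dose proportional to duration^b. The log variances are ln(1.25) = 0.223 and ln(1.16) = 0.148. Unadjusted variance is 0.223 + b² × 0.148. With log duration as a covariate it is 0.223, with one degree of freedom spent and an inflation of 1 + 1/84. Two-sided 5%, noncentral t:

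| b | Unadjusted variance | Power unadjusted | Power adjusted |
|---|---|---|---|
| 1 | 0.372 | 59.1% | 80.2% |
| 0.5 | 0.260 | 74.4% | 80.2% |
| 0 | 0.223 | 80.6% | 80.2% |

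Over hourly CV 0.4 to 0.6 and duration CV 0.3 to 0.5, the gain is 10 to 34 points for b = 1 and 2 to 9 for b = 0.5. For b = 0 there is a loss of at most 0.5 point. The documents do not say which b applies.

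**Validity.** In simulations with no treatment effect (2,000 runs per cell, 0 to 75% zeros, duration CV 0.3 or 0.6), type I error lay between 4.2% and 6.1% for every version, including Wilcoxon on raw totals with tied zeros.

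**Zeros.** The natural substitute for a zero-heavy dose is any use, yes or no, by chi-square or Fisher. Simulated on the assumptions above with b = 1, 44 per group and ratio 0.75 among users (about a point of simulation error; the any-use powers for 60% vs 40% and 60% vs 30% are exact):

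| Users, control vs study | Wilcoxon on dose | Chi-square | Fisher |
|---|---|---|---|
| 88% vs 88% (12% zeros) | 37% | 6% | 2% |
| 80% vs 80% | 27% | 6% | 3% |
| 60% vs 60% | 13% | 5% | 3% |
| 60% vs 40% | 64% | 45% | 36% |
| 60% vs 30% | 89% | 81% | 74% |
| 95% vs 80% | 83% | 62% | 47% |

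The rank test uses both who receives the drug and how much, and it has more power in every row. Power is low with many zeros only when the share of users is equal in both arms.

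**The case for a change.** The best case for a change is that the text lets two analysts build different outcomes. The investigators are unblinded (section 5.0) and each comparison is tested at 5%, so grouping, covariates and zero handling could be settled after the data are seen. A few sentences and a conversion table would close this, and the maintenance times are already needed for the primary outcome.

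Part of this stands. The documents give no unit or conversion, and they tie no window or named test to vasopressor dose. But the ordinary reading is available. Doses can be reported drug by drug. Section 3.2 calls all nine agents hypnotics, so the named test reaches the opioids. The general rule for continuous variables serves for vasopressors, and one window can be applied to both arms from the same record. Conversion factors would themselves be approximate.

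On zeros, the plan allows nonparametric tests, and the logarithm is only an example. On duration, the possible gain is real, but maintenance length is measured after randomisation. If it were 5% shorter in the study group (assumed) and dose proportional to time, a ratio of 0.75 at equal duration would appear as 0.75 × 0.95 = 0.71 unadjusted. The two analyses then answer different questions, and keeping the unadjusted one with the model alongside is defensible.

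**Conclusion.** No change is called for. The missing unit, grouping and vasopressor window are gaps that analysts would fill sensibly; the plan states no wrong method. Zero doses are already served by the rank test, and an any-use comparison in its place would lose power: 31 points (37% to 6%, chi-square) at 12% zeros in both arms, and 19 points (64% to 45%) for 60% against 40% users. Committing the duration covariate is a fair trade-off. It would gain 2 to 34 points of power if dose grows with time and nothing if it does not, in exchange for adjusting by a variable measured after randomisation that the plan already permits.

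These sizes rest on assumed CVs, an assumed 25% reduction among users and 44 per group. The anesthesiologist effect was not simulated. The effect is confined to the precision and presentation of secondary outcomes. The primary comparison, its sample size and the type I error of the planned tests are unaffected.

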We will identify subjects who meet inclusion/exclusion criteria on the day of surgery. Following explanation of the study and completion of informed consent, the patient will be randomized into 1 of 2 groups – study group or control group. We plan to use block randomization to keep the groups relatively balanced throughout enrollment. The patient will then be taken to the operating room in normal fashion. Prior to the induction of anesthesia, the Sedline monitor will be placed on the patient's head to ensure the monitor is working properly. For those in the study group, the monitor will be in full view of the anesthesiologist administering the anesthetic. For those in the control group, an apparatus will be placed over the monitor will not be in view of the anesthesiologist. The monitor will still be processing and recording EEGs for both groups. The patient will then be placed under anesthesia and surgery will commence. While under anesthesia, images of the display screen of the Sedline will be collected for later evaluation. Once the surgery is complete, the patient will have the monitor removed and image capture of the display will be stopped prior to exiting the operating room.

Following finalization of the anesthetic record by the staff anesthesiologist, the primary and secondary outcomes will be collected by investigators. The images of the Sedline EEG monitor will also be reviewed by investigators to ensure that appropriate depth of anesthetic was utilized throughout the maintenance phase of anesthesia in the study group. Blinding of the study investigators will not be possible due to the manner in which images of the Sedline readings are collected (it will be readily apparent on the images whether the SedLine data was readily available or concealed from the anesthesia team).

Prior to Enrollment

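### Section 12 lets surgery duration, known only after randomisation, into the adjusted model for sevoflurane percent, and leaves surgery type, known beforehand, uncommitted

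*Combined protocol and SAP*

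**What the plan says.** Section 12.0 first states that the primary outcome "will be compared between the two groups using t-test or Wilcoxon rank sum test as appropriate". To allow for age, sex, BMI and anesthesiologist, it then says "a mixed model with a random effect for anesthesiologists will be employed", and continues: "Here we could treat surgery type and duration as fixed effects if needed". It gives no trigger for that option, does not define duration, and does not say whether the unadjusted test or the mixed model is primary.

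Three other places bear on the point:

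- **Surgery type is known before allocation.** Section 4.1 makes the scheduled procedure an inclusion criterion: "Patients undergoing a scheduled surgery (laparotomy, hepatobiliary surgery, gynecologic surgery, and/or urologic surgery procedures".
- **Duration follows allocation.** In section 5.0, after consent on the day of surgery, "the patient will be randomized into 1 of 2 groups", and only afterwards: "The patient will then be taken to the operating room in normal fashion".
- **Surgery type is expected not to matter.** Section 5.0 anticipates that procedures will be similar enough that "the type of surgical procedure will not affect anesthetic dosing", yet section 12.0 keeps adjustment for it as an option.

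**The concern.** Adjusting for a covariate fixed before allocation leaves the randomised comparison intact and usually sharpens it. A variable observed after allocation is safe only if the arm does not affect it. Actual duration is of the second kind. The anesthesiologist knows the arm ("For those in the study group, the monitor will be in full view of the anesthesiologist administering the anesthetic"; in the control group the screen is covered) and titrates in response. Duration also plausibly shares causes with dose, such as case complexity. If the arm shifts duration at all, the adjusted coefficient mixes the effect of SedLine on sevoflurane with its effect on case length.

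Duration is not needed as an exposure correction either. The section 3.1 outcome is already an average percent over the maintenance phase, not a cumulative amount.

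Because no trigger is given, the covariate set could be chosen after the data are seen, in a trial whose investigators section 5.0 says cannot be blinded. Meanwhile surgery type, the covariate that could be added safely, is left uncommitted.

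**Working it through.** **1. The plan's own figure.** Inputs from section 12.0: CV 0.15, reduction 10%, two-sided 5%, power 90%, ratio-of-means test.

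- SD on the log scale = sqrt(ln(1 + 0.15²)) = 0.1492; effect = |ln 0.90| = 0.1054.
- The noncentral t gives power 89.9% at 43 per group and 90.6% at 44, so 44 reproduces.
- 44 / (1 − 0.20) = 55 per group reproduces.

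This calculation is for an unadjusted two-group test and does not change with the point made here.

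**2. Bias from adjusting for duration.** The documents give neither the spread of duration nor its correlation with dose. Assumed ranges: SD of log duration 0.30 to 0.60, within-arm correlation r of 0.3 to 0.5, SedLine cases 5% or 10% shorter, 44 per group, no true effect on dose.

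- Bias (log scale) = (r × 0.1492 / SD of log duration) × |ln(1 − shortening)|.
- Residual SD = 0.1492 × sqrt(1 − r²); standard error = residual SD × sqrt(2/44); error rate from the noncentral t.

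Example with SD 0.40, r = 0.5 and 10% shorter: bias = (0.5 × 0.1492 / 0.40) × 0.1054 = 0.0197, about 2.0% of dose, or 0.0197 / 0.1054 = 19% of the target effect. Residual SD = 0.1292, standard error = 0.0275, noncentrality = 0.71, two-sided error = 10.9%.

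| SD log duration | r | Shorter by | Bias, % of dose | Two-sided error | Of which false reduction |
|---|---|---|---|---|---|
| 0.60 | 0.3 | 5% | 0.4 | 5.2% | 1.9% |
| 0.40 | 0.3 | 5% | 0.6 | 5.4% | 1.6% |
| 0.40 | 0.3 | 10% | 1.2 | 6.7% | 1.0% |
| 0.40 | 0.5 | 10% | 2.0 | 10.9% | 0.4% |
| 0.30 | 0.5 | 10% | 2.6 | 15.6% | 0.2% |

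A simulation with a shared cause of dose and duration (6,000 runs, 88 patients) agreed at the fourth row: rejection 5.3% unadjusted and 10.6% adjusted for duration.

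**3. Direction.** With shorter SedLine cases and a positive correlation, the adjusted coefficient moves towards more sevoflurane under SedLine. In the fourth row about 10.5 of the 10.9 points are false increases. False reductions fall below the nominal 2.5% in every row. A false reduction needs one of the two signs reversed.

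**4. When the 10% reduction is real.** A second simulation (4,000 runs per setting, 44 per group, true ratio 0.90, path coefficients 0.3 to 0.5) gave:

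| Shortening of duration | Duration-adjusted ratio | Adjusted power |
|---|---|---|
| none | 0.90 | 92% to 95% |
| 0.1 SD | 0.903 to 0.906 | 90% to 93% |
| 0.25 SD | 0.909 to 0.915 | about 86% |
| 0.5 SD | 0.916 to 0.931 | 67% to 77% |

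The unadjusted ratio stayed at 0.90 throughout. For scale, 10% shorter cases at SD 0.40 is 0.1054 / 0.40 = 0.26 SD.

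**5. Surgery type.** If type explains a share R² of the variance, the SD becomes 0.1492 × sqrt(1 − R²). At 44 per group, power is 91.9% for R² = 0.05 and 93.2% for R² = 0.10, against 90.6% without it. These R² values are assumed, and the degrees of freedom used are ignored.

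**The case against.** The strongest reply is that the main comparison is not touched. Section 12.0 states the t-test or Wilcoxon comparison first, the sample size is built on an unadjusted test, and the mixed model can be read as supportive. That stands. A reader might infer that the trial's primary analysis is biased; the documents do not support this, because they name no primary model and the unadjusted test contains no covariate.

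Second, no passage suggests that SedLine alters case length. The guidance concerns sevoflurane titration, and section 7.0 has surgery going ahead in the usual way. That stands too: without an arm effect on duration, the adjustment is unbiased and gains some precision. A 10% shortening would be a sizeable knock-on effect for a monitor. But nothing in the plan rules out a smaller shift. If duration means anesthesia or maintenance time, the maintenance interval ends at neuromuscular blocker reversal, which is part of anesthetic care.

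Third, a reader might infer that the option favours a false claim of benefit. In the scenarios computed here it does the opposite.

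Fourth, duration might mean scheduled duration, which would be a legitimate baseline covariate. The text does not say so, and actual duration is the more natural reading.

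Finally, leaving out surgery type causes no bias in a randomised comparison, and section 5.0 gives a reason for expecting little from it. So committing it is a matter of precision and clarity, not validity.

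**Conclusion.** The point holds as a minor weakness of the optional covariate-adjusted model. Section 12.0 puts a pre-allocation and a post-allocation covariate on the same footing and gives no rule for using either. If the arm does not change case length, no bias follows. If SedLine cases are 5% to 10% shorter, the bias is about 0.4% to 2.6% of dose and the two-sided error about 5% to 16%, under the assumed spreads and correlations; with those signs the practical harm is masking a real reduction. The gain from committing surgery type is modest, to about 92% to 93% power from 90.6%, and also rests on an assumption. The planned 44 and 55 per group are unaffected.

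**What to change.** In section 12.0, replace the sentence on surgery type and duration with:

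> The adjusted mixed model for sevoflurane percent will include surgery type (section 4.1 categories, sparse ones merged) as a fixed effect with age, sex and BMI, and a random effect for anesthesiologist. Actual surgery duration will not be a covariate in this model; it will be summarised by arm, and any duration-adjusted model will be labelled a sensitivity analysis.

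This needs no new data, patients or procedures. The cost is a few degrees of freedom for surgery type. The summary of duration by arm will also show whether the concern has any practical weight in this trial.

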1.0 Background & Rationale

Electroencephalography (EEG) was first described in 1875 in dogs and apes.¹ The technology was shortly after applied to humans and within 10 years the changes to the EEG tracing was studied when certain sedatives drugs were administered.¹ Over the last several decades EEG based monitors have been developed with the hopes of aiding anesthesiologists at evaluating the “depth” of a patient’s anesthetic while under general anesthesia. Currently, typical anesthesia practice is to measure and adjust depth of a general anesthetic based on the medications administered and hemodynamic parameters of the patient, potentially exposing high risk patients to un-needed excessive depths of anesthesia which can potentially result in adverse post-operative outcomes.^{2,3}

The use of intraoperative EEG monitoring to guide the depth of an anesthetic seems to have the potential to reduce the total dose of anesthetic required. Use of the EEG based monitor called the Bispectral Index Monitor (BIS Monitor) in an older study was shown to reduce sedative use and total cost in ICU patients who were receiving intravenous infusions of sedatives and neuromuscular blockers.⁴ And recently, the BIS monitor was used in a large randomized control study in order to investigate whether providing an anesthetic guided by an EEG based monitoring device in individuals at high risk for postoperative delirium would significantly reduce postoperative delirium. While the primary results reported a negative results, the study did have other interesting findings – most notably a significant reduction in the dosage of volatile anesthetic (the primary anesthetic agent used in general anesthetic procedures). Furthermore, the study showed using a protocolized adjustment in anesthetic depth using an EEG based monitoring system for guidance in human subjects resulted in no significant change in adverse outcomes in a large trial of patients in this population⁵

The Masimo Sedline Brain Function Monitor (SedLine), is an EEG based monitoring device that is approved by the Food and Drug Administration for monitoring of brain function under anesthesia. This new generation device provides processed EEG information (as the BIS monitor does) as well as raw EEG waveforms and a Density Spectral Array (DSA) display – providing information of the power of the EEG signal over a spectrum of frequencies. This additional

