3.0 Outcome Measures/Endpoints

3.1 Primary Outcome Measures

The primary outcome measured will be the total average percent of volatile anesthetic (sevoflurane) utilized while subjects are under anesthesia (maintenance phase). The time considered “maintenance phase” under general anesthesia will be measured starting 5 minutes after the induction agents are administered and measurements will stop following

administration of neuromuscular blocker reversal drugs. Data will be collected from computerized anesthetic records.

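### Episodes of hypotension are tested only as any versus none, so their number is never compared, and the outcome carries no maintenance-phase window (minor, secondary outcome, cheap to improve)

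*Combined protocol and SAP*

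**What the plan says.** Section 3.2 names episodes of hypotension as a secondary outcome and gives a threshold: "this will be defined as an episode of mean arterial pressure of <65 mmHg". It also settles the source of the readings: where an arterial line is working, "we will use measurements from this in preference to a non-invasive blood pressure cuff". It gives no rule for when one episode ends and the next begins, and no time window.

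Section 12.0 repeats the outcome in the plural and assigns one analysis: "The secondary outcome of episodes of hypotension which will be compared using chi-square tests" or Fisher's "exact test for the occurrence of hypotension". The sentence on the t-test or Wilcoxon test covers sevoflurane percent and hypnotic dose. The later sentence on transformations and nonparametric tests concerns continuous variables in general and names no episode count.

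The maintenance phase is defined in section 3.1 under the primary outcome: time "under general anesthesia will be measured starting 5 minutes after the induction agents are administered", ending after reversal of neuromuscular block. Sections 3.2 and 12.0 attach it to the hypnotic doses, not to hypotension.

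**The concern.** The outcome's name promises a quantity, and the test reduces it to yes or no. A patient with one low spell and a patient with ten give the same result. The planned test can therefore detect first episodes that are prevented, but not fewer repeat episodes among patients who have at least one. For burst suppression, by contrast, section 3.2 intends to compare both rates and duration.

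Without a window, a low reading just after induction, before the primary outcome's clock starts, could turn a patient with no maintenance-phase hypotension into a yes.

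What is at stake is modest. If most patients have at least one low spell, a non-significant result could be reported under the heading of episodes although their number was never examined.

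**Working it through.** **The plan's own figure.** The only sample size is for sevoflurane. On the log scale, SD = sqrt(ln(1 + 0.15²)) = 0.1492 and the difference is |ln 0.90| = 0.1054. With 44 per group, the noncentral t gives 90.6% power (43 gives 89.9%), and 44/(1 - 0.20) = 55. The stated 44 and 55 reproduce. No figure is stated for hypotension.

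**Inputs.** From section 12.0: 44 evaluable per arm and a 5% level, taken as two-sided. Everything else is assumed: 40% fewer episodes in the study group, and gamma-Poisson counts with dispersion k from 0.5 to 2. Control occurrence is set at 20%, 50% or 80%.

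**Where the reduction goes.** With mean m episodes, P(any) = 1 - (1 + km)^(-1/k). For k = 1 and equal exposure, per 100 patients:

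| Control any | Mean, control to study | Study any | Fewer episodes | Fewer patients with any |
|---|---|---|---|---|
| 20% | 0.25 to 0.15 | 13.0% | 10 | 7.0 |
| 50% | 1 to 0.6 | 37.5% | 40 | 12.5 |
| 80% | 4 to 2.4 | 70.6% | 160 | 9.4 |

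The commoner hypotension is, the more of the reduction lies in repeat episodes, which the planned test does not count.

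**Power of the planned test by formula.** At 50% v 37.5%, the pooled proportion is 0.4375. SE0 = sqrt(2 × 0.4375 × 0.5625/44) = 0.1058 and SE1 = sqrt((0.25 + 0.2344)/44) = 0.1049. Then (0.125 - 1.96 × 0.1058)/0.1049 = -0.784, so power is 0.216. The same steps at 80% v 70.6% give 0.173.

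**Simulated power, any-versus-none against Wilcoxon on episodes per hour (range over k = 0.5 to 2).**

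| Control any | Any v none | Episodes per hour |
|---|---|---|
| 20% | 0.11-0.15 | 0.11-0.14 |
| 50% | 0.15-0.22 | 0.22-0.29 |
| 80% | 0.08-0.25 | 0.22-0.56 |

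A separate simulation of raw counts with equal exposure and k = 1 agrees: 0.215 v 0.284 at 50%, and 0.192 v 0.407 at 80%. Only with no extra-Poisson variation does the count test pass 0.80 (0.803 at a control mean of 2, 0.982 at 4). That would require every patient in an arm to share one underlying rate, which is unlikely here.

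**The window.** Suppose a share q of patients, equal in both arms, has a low reading outside maintenance. Observed occurrence is then 1 - (1 - p)(1 - q). At 50% control occurrence, the study-group p is 0.358 (k = 0.5) to 0.402 (k = 2), a gap of 10-14 points. With q = 0.2 the control figure is 1 - 0.5 × 0.8 = 60% against 49-52%, a gap of 8-11 points. With q = 0.4 it is 70% against 61-64%, a gap of 6-8.5 points. Both values of q are assumed.

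**The case against.** The strongest reply is that section 12.0 does specify an analysis. It says occurrence, and chi-square or Fisher's exact test is the right kind of test for occurrence. That stands. A reader might infer that the planned test is invalid; the documents do not support this. The test leaves out information and does not match the outcome's name, and that is all.

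A reader might also infer that the plan cannot detect any benefit on hypotension, or that a count analysis would rescue it. Neither follows. First episodes could be prevented by the EEG rules of section 5.0 (sevoflurane is reduced "if the EEG indicates signs of burst suppression (excessive anesthetic depth), if the PSI on the Sedline reads less than 25"), and the planned test would register them. The count test is also weak in the overdispersed scenarios tabulated, and gains nothing at 20% occurrence.

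Nor should section 5.0's hypotension trigger be read as a built-in difference between arms. Section 1.0 states that "typical anesthesia practice is to measure and adjust depth of a general anesthetic based on the medications administered and hemodynamic parameters of the patient", so controls may be adjusted on blood pressure too.

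The window gap is mostly a matter of clarification. Section 5.0 says that once the anesthetic record is final "the primary and secondary outcomes will be collected by investigators", so the period is implicitly intraoperative. Only its start and end are open, and the dilution shown above depends on assumed rates.

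Minutes below 65 mmHg might look like a better burden measure. It does not test the number of episodes, it needs timed pressures, and it also depends on the recording interval. It can only be an optional extra.

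**Conclusion.** The point holds as a minor, inexpensive improvement to one secondary outcome. The number of episodes is named but never tested, and the section 3.1 window is not attached. The size of the loss depends on an occurrence rate, an effect and a dispersion that the documents do not give. Under the assumptions above it runs from nothing at 20% control occurrence to about a doubling of power or more at 80% (0.08-0.25 against 0.22-0.56). Because neither test reaches 0.80 in those scenarios, a non-significant result on either must not be read as no difference. A reader might infer that the trial's main conclusion is exposed; it is not, since the primary outcome and the 44 and 55 per group are unaffected.

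**What to change.** In section 12.0:

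1. Keep the planned chi-square or Fisher's exact test and label it any occurrence of hypotension.
2. Add one pre-specified comparison of the number of episodes per patient per maintenance hour. Use either the Wilcoxon rank sum test or negative-binomial regression with log maintenance time as offset, and name which one before outcomes are compared. State that consecutive low readings count as one episode.
3. Count episodes within the section 3.1 maintenance phase for both analyses.

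Minutes below 65 mmHg may be added only if timed pressures can be exported.

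The cost is a few sentences, one more unadjusted secondary test at 5%, and an episode count plus maintenance time per patient from the anesthetic record (2 × 110 = 220 values). The documents do not say what is extracted for hypotension, so someone must confirm that episodes can be counted from the record. If they cannot, steps 1 and 3 still make the label and the window clear. Fixing the choice now also matters because section 5.0 states that the investigators cannot be blinded. The primary outcome and sample size do not change.
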